ARMS2	Age-related maculopathy susceptibility 2
AST	aspartate aminotransferase
BCVA	best corrected visual acuity
BMI	body mass index
BP	blood pressure
bpm	beats per minute
C3GN	C3 glomerulonephropathy
CFH	Complement Factor H
CFP	color fundus photography
CFR	code of federal regulation
CK	creatinine kinase
CNV	choroidal neovascularization
CRC	central reading center
CSM	clinical site manager
CSR	clinical study report
CV	coefficient of variation
DDD	dense deposit disease
DNA	deoxyribonucleic acid
ECG	electrocardiogram
eCRF	electronic Case Report Form
EDC	electronic data capture

Novartis
Amended Protocol Version No. 01 (Clean)

Confidential

Page 8
Protocol No. CCLG561X2201A

ELISA	enzyme-linked immunosorbent assay
EOS	end of study
ESI	event of special interest
ETDRS	early treatment diabetic retinopathy study
Fab	fully-human antibody
FA	fluorescein angiography
FAF	fundus autofluorescence
FU	follow up
GA	geographic atrophy
GCP	good clinical practice
GGT	gamma-glutamyl transferase
GLP	good laboratory practice
HIV	human immunodeficiency virus
HTRA1	high temperature requirement A serine peptidase 1
IAG	image acquisition guidelines
IB	Investigator's brochure
IC50	inhibitor concentration 50%
ICH	international conference on harmonization
IEC	independent ethics committee
Ig	immunoglobulin
IOP	intraocular pressure
IRB	Institutional Review Board
IRC	independent review charter
IRT	interactive response technology
IVT	Intravitreal
IV	Intravenous
kg	kilogram
LASIK	laser-assisted in situ keratomileusis
LDH	lactate dehydrogenase
LLN	lower limit of normal
LLOQ	lower limit of quantification

Novartis
Amended Protocol Version No. 01 (Clean)

Confidential

Page 9
Protocol No. CCLG561X2201A

MedDRA	medical dictionary for regulatory activities
mg	milligram(s)
mL	milliliter(s)
mmHG	millimeters of mercury
MMRM	mixed-effect model repeated measure
MOP	manual of procedures
MPGN II	membranoproliferative glomerulonephritis type II
N or n	sample size
NEI VFQ-25	National Eye Institute Visual Functioning Questionnaire – 25
nM	nanometer
No.	number
NOAEL	no observed adverse effect level
OD	Right eye
OS	left eye
PD	pharmacodynamic(s)
pH	negative log of the activity of the hydrogen ion in an aqueous solution
PK	pharmacokinetic(s)
pM	picometer
POC	proof of concept
PP	per-protocol
PRK	photorefractive keratectomy
PT/INR	prothrombin time/international normalized ratio
q2w	biweekly
q4w	every 4 weeks
RBC	red blood cell(s)
RPE	retinal pigment epithelium
SAD	single-ascending dose
SAE	serious adverse event
SD	standard deviation
SD-OCT	spectral domain optical coherence tomography
SNP	single nucleotide polymorphism

Novartis

Confidential

Page 10

Amended Protocol Version No. 01 (Clean)

Protocol No. CCLG561X2201A

ULOQ	upper limit of quantification
VEGF	vascular endothelial growth factor
WBC	white blood cell(s)
WHO	world health organization

Novartis

Confidential

Page 11

Amended Protocol Version No. 01 (Clean)

Protocol No. CCLG561X2201A

Pharmacokinetic definitions and symbols

AUC	The area under the plasma (or serum or blood) concentration-time curve
Cmax	The observed maximum plasma (or serum or blood) concentration following drug administration [mass / volume]
Tmax	The time to reach the maximum concentration after drug administration [time]

Alcon - Business Use Only Protocol - Clinical

Document: TDOC-0050366

Status: Effective

Effective Date: 20-Jan-2016

Version: 2.0; Most-Recent; Effective; CURRENT

Novartis

Confidential

Page 12

Amended Protocol Version No. 01 (Clean)

Protocol No. CCLG561X2201A

Corporate Confidential Information

Alcon - Business Use Only Protocol - Clinical

Document: TDOC-0050366

Version: 2.0; Most-Recent; Effective; CURRENT

Status: Effective

Effective Date: 20-Jan-2016

Novartis

Confidential

Page 13

Amended Protocol Version No. 01 (Clean)

Protocol No. CCLG561X2201A

Corporate Confidential Information

Alcon - Business Use Only Protocol - Clinical

Document: TDOC-0050366

Version: 2.0; Most-Recent; Effective; CURRENT

Status: Effective

Effective Date: 20-Jan-2016

Corporate Confidential Information

Alcon - Business Use Only Protocol - Clinical

Document: TDOC-0050366

Status: Effective

Effective Date: 20-Jan-2016

Version: 2.0; Most-Recent; Effective; CURRENT

Novartis

Confidential

Page 15

Amended Protocol Version No. 01 (Clean)

Protocol No. CCLG561X2201A

Corporate Confidential Information

C

Alcon - Business Use Only Protocol - Clinical

Document: TDOC-0050366

Status: Effective

Effective Date: 20-Jan-2016

Version: 2.0; Most-Recent; Effective; CURRENT

Novartis

Confidential

Page 16

Amended Protocol Version No. 01 (Clean)

Protocol No. CCLG561X2201A

Corporate Confidential Information

Alcon - Business Use Only Protocol - Clinical

Document: TDOC-0050366

Status: Effective

Effective Date: 20-Jan-2016

Version: 2.0; Most-Recent; Effective; CURRENT

C

Novartis

Confidential

Page 17

Amended Protocol Version No. 01 (Clean)

Protocol No. CCLG561X2201A

Corporate Confidential Information

Novartis

Confidential

Page 18

Amended Protocol Version No. 01 (Clean)

Protocol No. CCLG561X2201A

Protocol synopsis

Protocol number	CCLG561X2201A(CLG561-2201)
Title	A randomized, multi-center, single masked, sham controlled, proof-of-concept study of intravitreal CLG561 as a monotherapy and in combination with LFG316 in subjects with geographic atrophy
Brief title	CLG561 (anti-properdin) proof-of-concept study as a monotherapy and in combination with LFG316 (anti-C5) for subjects with geographic atrophy (GA).
Sponsor and clinical phase	Alcon Research, Ltd., a Novartis company Phase II
Intervention type	Biologic
Study type	Interventional
Purpose and rationale	To identify whether CLG561 as a monotherapy and in combination with LFG316 has the desired clinical profile in treatment of GA to warrant further development.
Primary Objectives	
 To evaluate the safety of 12 (every 28 days) IVT injections of CLG561 as a monotherapy and in combination with LFG316 as compared to sham To evaluate in the study eye the efficacy of 12 (every 28 days) IVT injections of CLG561 as a monotherapy and in combination with LFG316 as compared to sham on the growth of GA lesion size as assessed by FAF based on the change from baseline to Day 337
Secondary Objectives	
 To evaluate the time course of the change in GA lesion size of the active arms as compared to sham as measured by FAF in the study eye To evaluate the time course of the change in BCVA/low luminance visual acuity/low luminance visual acuity deficit up to Day 337 of the active arms as compared to sham in the study eye To evaluate the average change in BCVA/low luminance visual acuity/low luminance visual acuity deficit from baseline to the period Day 281 to Day 337 of the active arms as compared to sham in the study eye To evaluate the time course of the proportion of study eyes losing or gaining ≥ 15 letters, ≥ 10 letters, and ≥ 5 letters in BCVA from baseline up to Day 337 in each of the active arms as compared to sham in the study eye To describe: 
 The systemic exposure of total CLG561 after IVT administration of CLG561 as a monotherapy up to Day 421 The systemic exposure of total CLG561 and total LFG316 after IVT administration of CLG561 in combination with LFG316 up to Day 421 To describe the immunogenicity of CLG561 after IVT administration of CLG561 as a monotherapy and the immunogenicity of CLG561 and LFG316 after IVT administration of CLG561 in combination with LFG316 up to Day 421

Alcon - Business Use Only Protocol - Clinical

Document: TDOC-0050366

Version: 2.0; Most-Recent; Effective; CURRENT

Status: Effective

Effective Date: 20-Jan-2016

Novartis

[figure not shown]
Confidential

Page 19

Amended Protocol Version No. 01 (Clean)

Protocol No. CCLG561X2201A

Corporate Confidential Information

Study design	
This study employs a multi-center, randomized, sham-controlled, single-masked design. Approximately 114 eligible subjects with GA will be randomized in a 1:1:1 ratio to obtain approximately 90 evaluable subjects completing the study per protocol. Subjects will receive one of three treatment modalities:
 
 1. CLG561 (10 mg/100 µL) 2. CLG561 (5 mg/50 µL) + LFG316 (5 mg/50 µL) 3. Sham injection 
The treatment modalities will occur every 28 days for a total of 12 injections (or sham injections).
  <pre> graph LR A[AMD patients with GA] --> B[Screening] B --> C[Eligibility] C --> D[Randomization Treatment Arm (1:1:1)] D --> E[CLG561 10 mg IVT injection (every 28 days x 12)] D --> F[CLG561 5 mg + LFG316 5 mg IVT co injection (every 28 days x 12)] D --> G[Sham injection (every 28 days x 12)] E --> H[Treatment (D1-D336)] F --> H G --> H H --> I[FU/EO5 (D337-D421)] </pre> 
Randomization is performed within an IRT system. The IRT will randomize the subject into 1 of 3 treatment modalities.
 
The following are masked to treatment assignment:
 
 • Subjects • Visual acuity assessor at the study site • Technicians obtaining images at the study site • CRC staff 
Both eyes must have GA. Only one eye must meet the other inclusion/exclusion criteria to be eligible for study participation. Randomization is 1:1:1 (CLG561: CLG561 + LFG316: Sham Injection).
 
The study consists of up to 30-Day screening period, approximately 336-Day treatment period (12 IVT injections occurring approximately every 28 days), and a follow up period consisting of two visits occurring 4 and 16 weeks after the last administered injection.
 
If a subject prematurely exits the study, then he/she must return to the clinical site approximately 4 weeks after their last injection (or the earliest possible date after 4 weeks) for the end of study (EOS) evaluation. In this case, all assessments must be completed at the EOS visit.

---------------------	--

Population	
Male or female subjects (≥ 50 years old) with GA are deemed most appropriate for this study for the following reasons:
 
 Both CLG561 and LFG316 are being developed for subjects with GA Due to reduced visual acuity, eyes with GA are less likely to sustain incremental loss of visual acuity from an ocular AE Eyes with GA may experience a benefit from CLG561 monotherapy or in combination with LFG316 Administration of multiple doses of CLG561 as a monotherapy and in combination with LFG316 to eyes with GA will provide information regarding the efficacy of monotherapy with CLG561 or its combination with LFG316 The age range of subjects over 50 corresponds to the typical age range of the subjects with advanced AMD 
The study plans to recruit approximately 114 subjects (38 in each treatment arm) in order to yield 30 evaluable subjects in each treatment arm.

Inclusion criteria	
Subjects eligible for inclusion in this study have to fulfill all of the following criteria:
 
 Able and willing to provide written informed consent and in the opinion of the Investigator, the subject is able to complete the duration of the study. Note: Informed consent must be obtained before any assessment is performed Male or female GA subjects ≥ 50 years of age GA in BOTH EYES. One eye MUST meet the following criteria with lesion size assessed by FAF and measured by the CRC. 
 IF GA lesion is multifocal, THEN the total lesion area must be between 3-16 mm² and at least one lesion with an area of at least 1.25 mm² IF GA lesion is unifocal, THEN the lesion area must be between 8-16 mm² Presence of hyper-autofluorescence adjacent to at least 10% of perimeter of GA in the study eye Best-Corrected Visual Acuity of 20/20 or worse in both eyes at Screening
Exclusion criteria	
Subjects fulfilling any of the following criteria are not eligible for inclusion in this study. No additional exclusions may be applied by the Investigator, in order to ensure that the study population will be representative of all eligible subjects.
 
 Pregnant or lactating women and women of child-bearing potential (defined as all women physiologically capable of becoming pregnant). Women are considered post-menopausal and not of child bearing potential if they have had: 
 12 months of natural (spontaneous) amenorrhea with an appropriate clinical profile (e.g. age appropriate, history of vasomotor symptoms) Total hysterectomy Surgical bilateral oophorectomy (with or without hysterectomy) Tubal ligation for at least six weeks Oophorectomy alone is acceptable ONLY when the reproductive status of the woman is confirmed by follow up hormone level assessments and she is considered to be not of child bearing potential Subjects demonstrating any medical condition (systemic or ophthalmic) that may, in the opinion of the Investigator, and based on the content of the IB, preclude the safe administration of test article or safe participation in this

Novartis

Confidential

Page 22

Amended Protocol Version No. 01 (Clean)

Protocol No. CCLG561X2201A

	
 3. Any contraindications or hypersensitivities to any component of the LFG316 or CLG561 solution 4. Any contraindications to IVT injections 5. Retinal disease, other than AMD, in either eye Note: Benign conditions of the vitreous or peripheral retina are NOT excluded. Significant peripapillary atrophy either present at the time of Screening or which is expected to merge with the GA lesion during the course of the study IS excluded. 6. Any history of, or current evidence of, CNV in either eye, as determined by FA at screening 7. Media opacity that interferes with fundus imaging in either eye, or is likely to require surgery during the study period 8. Any active ocular or periocular infection or active intraocular inflammation in either eye at screening or at baseline (e.g., infectious blepharitis, infectious conjunctivitis, keratitis, scleritis, endophthalmitis) 9. Any history of the following in either eye at screening: 
 • herpes simplex keratitis • herpes zoster keratitis • infectious uveitis 10. Penetrating ocular surgery requiring cutting of ocular tissue (e.g., cataract surgery, PRK, LASIK, Epilasik, pterygium removal, etc.) or ocular trauma requiring medical or pharmacological treatment in the study eye within 90 days of screening. Note: Ocular laser procedures are not excluded 11. Macular atrophy in either eye due to anything other than AMD 12. Concomitant treatment for AMD in either eye within 90 days of screening Note: Concomitant use of vitamins/supplements is not excluded 13. Any periocular or IVT injections in either eye within 90 days of baseline 14. Any of the following abnormal vital signs at screening: temperature > 100.5° F (38° C); heart rate > 100 bpm; systolic blood pressure <90 mmHg or > 160 mmHg; diastolic blood pressure > 95 mmHg. Note: Out of range vital signs may be repeated once. If the values are still out of range the visit must be rescheduled. If out of range vitals are observed again and persistent at re measurement, the subject must be disqualified from the study. Subjects may be rescreened when values have stabilized. 15. Uncontrolled ocular hypertension or glaucoma in the study eye (IOP >25 mmHg despite current pharmacological or non-pharmacological treatment) 16. Participation in any interventional clinical trial within 12 weeks prior to screening 17. Any history of participation in interventional clinical trials involving gene therapy or extended release products, or any product with expected long term efficacy
--	---

Novartis

Confidential

Page 23

Amended Protocol Version No. 01 (Clean)

Protocol No. CCLG561X2201A

Investigational and reference therapy	
Investigational Products/Treatments:
 
CLG561 (anti-properdin Fab)
 
 • IVT Injection • 10 mg/100 µL • Every 28 days for total of 12 injections 
CLG561 (anti-properdin Fab) combined with LFG316 (anti-C5 IgG)
 
 • IVT Injection (co-injection) • CLG 561 5 mg/ 50 µL mixed with LFG316 5 mg/ 50 µL (total 100 µL) are mixed in a vial and will be administered as a 100 µL total volume via a single syringe • Every 28 days for total of 12 injections 
Control Products/Treatments:
 
 • Sham injections • Hub of an empty syringe (without a needle) will be placed against the eye • Every 28 days for total of 12 sham-injection procedures
Efficacy /PK/PD assessments	
 • GA lesion as measured by FAF (both eyes) • BCVA (both eyes) • Low luminance visual acuity (both eyes) • Serum concentration of total CLG561 and total LFG316 • Serum levels of anti-drug antibodies (ADA; anti-CLG561 and anti-LFG316 antibodies) 
Corporate Confidential Information

Safety assessments	
 • AEs (AEs) (incidence, severity, overall assessment) • Vital signs (blood pressure, heart rate) • Laboratory evaluations • Hematology • Chemistry including liver function tests • Urinalysis • Complete ophthalmic exam (slit lamp, dilated fundus exam, BCVA, IOP) 
Corporate Confidential Information

Other assessments	

Data analysis	
Primary Endpoint Change in GA lesion size from baseline to Day 337
 
Hypotheses One-sided hypotheses of superiority of active related to the comparison of each of the two active arms vs control (sham injections). The comparison of the two active arms will be done descriptively.
 
Primary analysis data set The primary efficacy analysis data set is a per-protocol (PP) set. Key PP criteria are compliance with the GA specific inclusion criteria, the monthly injection schedule up to Day 337 (not missing greater than 1 in any 6 months period or not missing 2 consecutive doses) and available baseline and Day 337 and/or Day 253 lesion size assessments. Missing values of lesion size on Day 337 will be imputed based on linear regression/extrapolation.
 
Statistical testing strategy For hypotheses-testing a global one-sided alpha of 0.2 is considered. With the two hypotheses being tested in parallel using the Bonferroni multiplicity adjustment, the nominal one-sided alpha for each single hypothesis will be 0.1.
 
Statistical method The lesion size change from baseline to Day 337 will be analyzed by an ANOVA model including but not limited to the class variable representing categories of baseline lesion size (edge length) and categories of lesion location.
 
Sample size A sample size of 30 per-protocol (PP) evaluable subjects per treatment arm will allow identification of a treatment difference of 0.67 mm² in lesion size change from baseline to Day 337 (representing a 33% reduction in lesion growth rate, assuming an average natural disease progression of 2.0 mm² per year) at a one-sided alpha level of 0.1 with a power of 80% assuming a standard deviation of 1.2 mm². In anticipation of a drop-out /protocol deviation rate of 20%, a total sample size of ~114 randomized subjects (~38 subjects/arm) is planned for the current study to ensure sufficient study completers for the above described PP analysis. Depending on ongoing monitoring of the drop-out/protocol deviation rate the need for additional recruitment will be assessed to ensure 90 PP evaluable subjects are available for the Day 337 analysis.

Key words	Geographic atrophy, GA, macular degeneration, dry AMD, IVT, intravitreal, retinal diseases, FAF

1 Introduction

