A hallmark of AMD is the development of drusen, which are lipoproteinaceous deposits located between the retinal pigment epithelium and Bruch's membrane and can be a risk factor for disease progression. In membranoproliferative glomerulonephritis type II (MPGN II), or more specifically C3 glomerulonephropathy (C3GN) and Dense Deposit Disease (DDD), systemic hyper-activation of the complement system, either by C3 nephritic factor or mutations in the complement regulatory protein factor H, leads to deposition of C3 activation products within the kidney glomerular basement membrane. Some patients with MPGN II also develop ocular drusen deposits within Bruch's membrane at early ages that resemble drusen seen in AMD patients and the patients may progress to vision loss ([Hageman et al 2001](#), [Appel et al 2005](#)).

Investigator led Phase 2 clinical trials with intravenously administered eculizumab (Alexion) (anti-C5 antibody) have been conducted in patients with GA or intermediate AMD (drusen).

Eculizumab was administered at two different doses to cohorts of patients either with intermediate AMD or GA for 6 months with a further follow up period of 6 months ([Yehoshua et al 2014](#), [Garcia Filho et al 2014](#)). The drug was well tolerated with no drug-related AEs. There were no differences between the GA lesion sizes or drusen volume in the treatments versus placebo groups at 6 months. The reasons for inability of eculizumab to demonstrate efficacy in GA or intermediate AMD may be due to the short duration of treatment, the route of administration (IV) of the compound, or the small numbers of patients.

More recently, Genentech presented their Phase 2 results with the anti-factor D Fab, lampalizumab, in patients with GA ([Regillo et al 2013](#)). They observed a 20.4% reduction in GA lesion growth in overall patients treated with monthly IVT injection of 10 mg of lampalizumab. The observed effect was larger (42%) in patients who had a complement factor I polymorphism.

In summary, there are multiple converging lines of evidence that AMD involves over-activation of the alternative complement cascade and provides a rationale for complement inhibition therapy.

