3.2 Rationale of study design

The design of this study will address the primary objectives of efficacy and safety of every 4 weeks IVT injection of monotherapy with CLG561 (10 mg), as well as the combination of LFG316 and CLG561 (5 mg of each) in subjects with GA. Since there is currently no product approved for the treatment of GA, no active comparator is included in the current study. The control for this study will be a sham injection, which is a common and well-established method of control for studies of IVT medications.

Subjects and certain study personnel, but not the Investigator or Sponsor, will be masked to treatment randomization. This approach was chosen for two reasons:

1. Opalescence of the IVT formulation is likely to be visible in the peripheral vitreous, particularly at early visits and would identify actively treated subjects to the study ophthalmologists
2. The primary endpoint is based on objective evaluations by a central reading facility, which will be masked to treatment assignment

Treatment randomization between the active arms and sham allows the evaluation of safety characters of CLG561 as a monotherapy and in combination with LFG316 in a balanced and objective manner. All study subjects will undergo the same study assessments and receive their assigned study treatments under the same dosing interval (every 28 days). All treatment arms will proceed in parallel to each other.

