3.3 Rationale of dose/regimen and duration of treatment

Rationale for treatment arms

Since GA is a slowly progressive disease, prolonged treatment and observation are required to detect any potential clinical efficacy with CLG561 as a monotherapy or combination of both CLG561 and LFG316. The every 28 day injection frequency is similar to the standard dosing frequency deployed in the LFG316 monotherapy study and in other GA studies conducted with anti-complement agents [the MAHALO trial by Roche testing every 4 week injection of lampalizumab (anti-factor D Fab)].

Based on power calculations, a 12-month treatment period is adequate to measure a clinically meaningful effect. This period of observation depends on available technology, which is currently FAF with semi-automated area quantification using RegionFinder software (Heidelberg Engineering).

Injection of the maximum deliverable concentration of CLG561 (10 mg) is supported by the 26-week IVT toxicity studies in cynomolgus monkeys. Injection of the maximum deliverable concentration of LFG316 (10 mg) is supported by the 26 week IVT toxicity studies in cynomolgus monkeys (605210) in accordance with ICHS6 (R1). The injection of 5 mg CLG561 and 5 mg LFG316 is supported by the 3 month intravitreal CLG561/LFG316 combination toxicology study in cynomolgus monkeys.

As there are no animal models of GA available, the dose-response relationship is unknown for CLG561 or its combination with LFG316. Thus it is proposed to test the highest safe dose of CLG561 (10 mg) as monotherapy. Further monotherapy dose ranging will take place in phase IIb/phase III studies. The combination of 5 mg of each molecule in 100 µL is the maximum feasible volume that can be safely delivered into the vitreous. The combination of CLG561 and LFG316 has shown synergistic efficacy *in vitro* inhibition of complement activation, and in an in vivo murine in vivo model of complement-dependent ocular inflammation. Thus, it is expected that the combination of CLG561 and LFG316 will have superior efficacy in GA as compared to monotherapy.

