11.5 Analysis of secondary and exploratory variables

11.5.1 Efficacy endpoints

Analyses will be performed for both the PP set and the FAS.

Potential treatment effects will primarily be assessed based on the difference in change from baseline in the study eye between active treatment and sham treatment. In addition, the corresponding difference between study and fellow eye will be explored within the active treatment arms.

At time points assessed, each efficacy endpoint will be presented graphically and by descriptive statistics provided for observed absolute values and changes from baseline. Changes from baseline will be compared between treatment arms using ANOVA models and/or stratified/unstratified Cochran-Mantel-Haenszel Tests.

Corporate Confidential Information

For treatment differences and differences between study and fellow eye 80% confidence intervals will be provided.

The following secondary endpoints will be evaluated:

- Change in geographic atrophy lesion size from baseline to Days 85, 169, 253, 337 and 421 as measured by fundus auto-fluorescence
- Change in BCVA, low luminance visual acuity and low luminance visual acuity deficit from baseline by visit up to Day 337 as measured by ETDRS in the overall population and in subsets of patients with baseline visual acuity < 73 letters
- Subject status regarding ≥ 15 letters, ≥ 10 letters, and ≥ 5 letters change from baseline in BCVA by visit up to Day 337
- Average change in BCVA/low luminance visual acuity/low luminance visual acuity deficit from baseline to the period Day 281 to Day 337

For the changes in geographic atrophy lesion size from baseline between either of the active arms and sham as measured by FAF, the same analysis model used for the primary hypothesis (Section 11.4.2) will be used.

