11.6 Sample size calculation

A sample size of 30 PP evaluable subjects per treatment arm will allow identification of a treatment difference of 0.67 mm^2 in lesion size change from baseline to Day 337 (representing a 33% reduction in lesion growth rate, assuming an average natural disease progression of 2.0 mm^2 per year) at a one-sided alpha level of 0.1 with a power of 80% assuming a standard deviation of 1.2 mm^2 .

In anticipation of a drop-out /protocol deviation rate of 20%, a total sample size of ~114 randomized subjects (~38 subjects /arm) is planned for the current study to ensure sufficient study completers for the above described PP analysis. Depending on ongoing monitoring of the drop-out / protocol deviation rate the need for additional recruitment will be assessed to ensure 90 PP evaluable subjects are available for the Day 337 analysis.

Corporate Confidential Information

12 Ethical considerations

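### Does testing each active arm at one-sided 0.1 by Bonferroni waste the global one-sided 0.2, so that a step-down test should replace it?

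*Protocol*

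**What the plan says.** The Data analysis row of the Protocol synopsis sets one-sided superiority hypotheses for each active arm against sham. On the error limit it says "For hypotheses-testing a global one-sided alpha of 0.2 is considered", and on the split "With the two hypotheses being tested in parallel using the Bonferroni multiplicity adjustment, the nominal one-sided alpha for each single hypothesis will be 0.1". The two active arms are compared with each other only descriptively (synopsis and Section 11.4.2).

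Section 11.6 sizes the study for a single comparison: 30 per-protocol evaluable subjects per arm, a difference of 0.67 mm², SD 1.2 mm², "at a one-sided alpha level of 0.1 with a power of 80" percent. Section 11.5.1, whose endpoint list includes the lesion change to Day 337, adds "For treatment differences and differences between study and fellow eye 80% confidence intervals will be provided".

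The visible text contains no step-down rule, hierarchy or passing-on of alpha. Part of Section 11.4.2, after the hypotheses, is blacked out, but the synopsis is explicit without it.

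**The concern.** A plan that names 0.2 as its global limit and then tests each arm at 0.1, whatever the other arm shows, seems to leave error allowance unused. Once one null hypothesis has been rejected, only one remains, and a step-down procedure may test it at the full 0.2. Holm does this. It rejects everything Bonferroni rejects, sometimes a second arm as well, and keeps the family-wise error within 0.2.

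The setting adds weight. Each regimen faces its own decision on further development (Section 1.2), and Section 3.3 says "it is expected that the combination of CLG561 and LFG316 will have superior efficacy in GA as compared to monotherapy". If that means two active arms of unequal strength, the weaker one is where single-step Bonferroni loses most. A regimen worth developing could then be missed more often than the global limit requires. One could also ask whether the real limit is 0.2 overall or 0.1 per arm, since the better test depends on the answer.

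**Working it through.** **Inputs** (synopsis; Sections 3.1 and 11.6): 30 evaluable per arm, SD 1.2 mm², effect 0.67 mm², one-sided 0.1 per test, global 0.2, allocation 1:1:1, 20% loss. Equal arms sharing one sham group give a correlation of 0.5 between the two test statistics. The calculation uses the normal approximation and omits the ANOVA class variables.

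**The plan's own figures**

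- n per arm = 2 × 1.2² × (1.2816 + 0.8416)² / 0.67² = 28.9, so 29; the plan has 30.
- SE = 1.2 × √(2/30) = 0.3098 and 0.67/0.3098 = 2.162. Power = Φ(2.162 − 1.2816) = 81.1% (80.8% with a t test on 87 df); the plan has 80%.
- 0.1 + 0.1 = 0.2. 30/0.8 = 37.5, so 38 per arm and 114 in all, as stated.

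**Validity of Bonferroni.** With both arms inert, P(any false success) = 0.100 + 0.100 − 0.0324 = 16.8%, within 20%. With one arm inert, its false-success rate is 10.0%.

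**Bonferroni against Holm.** Let c₁ = 1.2816 (level 0.1) and c₂ = 0.8416 (level 0.2).

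- P(Holm declares both) = P(Z₁>c₁, Z₂>c₂) + P(Z₁>c₂, Z₂>c₁) − P(Z₁>c₁, Z₂>c₁).
- P(Holm declares arm 2) = P(Z₂>c₁) + P(Z₁>c₁, Z₂>c₂) − P(Z₁>c₁, Z₂>c₁).

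Both arms at 0.67 mm²: both declared = 0.7646 + 0.7646 − 0.7021 = 0.8271. One arm at 0.67 mm², the other inert: inert arm declared = 0.1000 + 0.1923 − 0.0976 = 0.1947.

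| True effects (mm²) | Quantity | Bonferroni | Holm |
|---|---|---|---|
| 0.67 and 0.67 | both declared | 70.2% | 82.7% |
| | a given arm declared | 81.1% | 87.3% |
| | at least one declared | 92.0% | 92.0% |
| 0.67 and 0.41 | weaker arm declared | 51.7% | 65.2% |
| | both declared | 47.4% | 63.7% |
| 0.67 and 0 | effective arm declared | 81.1% | 81.3% |
| | inert arm declared | 10.0% | 19.5% |
| 0 and 0 | at least one declared | 16.8% | 16.8% |
| | a given arm declared | 10.0% | 11.9% |

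The 0.41 mm² is illustrative only. It applies another drug's result reported in Section 1.1 ("They observed a 20.4% reduction in GA lesion growth in overall patients") to the assumed 2.0 mm² growth: 0.204 × 2.0 = 0.41.

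**Observed difference needed to succeed.** At level 0.1 it is 1.2816 × 0.3098 = 0.40 mm², about 20% of 2.0 mm². At Holm's second step it is 0.8416 × 0.3098 = 0.26 mm², about 13%. The design effect is 33%.

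**Agreement with the 80% intervals.** A two-sided 80% interval leaves 10% in each tail, so it excludes zero in favour of active treatment exactly when the one-sided test at 0.1 rejects. Holm's extra rejections are therefore the cases in which the interval includes zero: 82.7 − 70.2 = 12.5% of trials with both arms at 0.67 mm², 63.7 − 47.4 = 16.3% at 0.67 and 0.41 mm², and 19.4 − 9.8 = 9.6% with one arm inert (19.4% and 9.8% being the chances that both arms are declared there).

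**The case for a change.** The best argument for a change takes the wording literally. The global 0.2 comes first and 0.1 is derived from it by the adjustment, so 0.2 is the declared limit. Measured against that limit alone, Bonferroni gives up 12.5 points of power to declare both arms at the design effect, and about 16 points in the illustrative unequal case, with nothing gained in return. Holm would cost one sentence and no subjects. Step-down Dunnett, with a first step at about 0.121, would also raise the power of a single effective arm to 84.1%. In a proof-of-concept study, missing an active regimen is a real loss.

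The arithmetic stands. Three things keep it from being a criticism of the plan.

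- Error per arm matters as well as error overall, because each regimen is judged for development separately. Holm's gain for a weaker active arm comes with a near doubling of false success for an inert one.
- Section 3.3 does not settle which case applies. An expectation that the combination beats monotherapy fits an inert monotherapy as well as a weakly active one, and Section 11.6 gives one effect size, 0.67 mm², without distinguishing the comparisons.
- No limit is left undefined. The synopsis gives the global level, the per-hypothesis level and the rule that links them, and anyone following it reaches one result.

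**Conclusion.** The concern does not hold. The testing strategy is valid, complete and consistent: global one-sided 0.2, Bonferroni, 0.1 per hypothesis, power at 0.1, and 80% intervals that match tests at 0.1. Family-wise error is at most 16.8% in the cases examined, and power per comparison is 81%.

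Holm is a legitimate alternative but not a correction. With both arms at 0.67 mm² it would declare both in 82.7% of trials instead of 70.2%. In exchange it would raise false success for an inert arm beside an effective one from 10.0% to 19.5%, let a second arm pass on about 0.26 mm² instead of 0.40 mm², and produce a declared arm whose 80% interval includes zero in roughly 10 to 16% of trials in the three scenarios with an effective arm. It would not change the chance of at least one success. Holding each regimen to 10% when the overall level is already lenient is a defensible choice.

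The figures rest on the plan's SD and evaluable numbers, equal arms, correlation 0.5 and the normal approximation. With both arms at 0.67 mm², a pooled t check on 87 df moves the Bonferroni and Holm results by at most 0.3 point.
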